5.6. Subgroup analyses

We will assess whether the effect of probiotic supplementation on the primary outcomes differs in the following subgroups, listed according to whether the subgroups are defined pre-randomisation or post-randomisation.

Pre-randomisation:

- prematurity (2 groups): <32weeks, 32-<37 weeks, among preterm infants only
- birth weight (3 groups): < 1.5kg, 1.5 to < 2.5kg, 2.5+ kg
- preterm and SGA status (2 groups): preterm SGA, preterm AGA among preterm infants only
- early initiation of enteral feeding (including mother's milk, donor milk, infant formula) (3 groups): within < 1hour, 2-< 24hour, 24+ hours after birth

Post-randomisation:

- vaccination according to vaccine schedule from enrolment to 6 months (3 groups): fully vaccinated, partially vaccinated, not vaccinated
- feeding type at 1 month of age (3 groups): exclusive, predominant, partial
- feeding type at 3 months of age (3 groups): exclusive, predominant, partial
- feeding type at 6 months of age (3 groups): exclusive, predominant, partial
- any micronutrient supplement intake from enrolment to 6 months of age (2 groups): any, none
- iron supplement intake from enrolment to 6 months of age (2 groups): any, none
- vitamin A supplement intake from enrolment to 6 months of age (2 groups): any, none
- vitamin D supplement intake from enrolment to 6 months of age (2 groups): any, none
- zinc supplement intake from enrolment to 6 months of age (2 groups): any, none
- receipt of antibiotics from enrolment to 6 months of age (2 groups): yes, no

For subgroups defined pre-randomisation, this will be done by summarising results separately for each sub-group, and fitting a regression model including an interaction term between trial arm and subgroup indicator, and presenting the effect of the intervention within each subgroup. Interaction terms will be assessed for strength of evidence against the null hypothesis of no effect modification, using likelihood ratio tests.

For subgroups defined post-randomisation, we acknowledge the risk of bias in these analyses. During the protocol development for the trial, there was considered to be plausible reasons why the effects of treatment could be different in the different subgroups. For example, probiotics have been shown to reduce infection rates in preterm infants and to promote vaccine responses in normal infants. Vaccines may modify the effect of the probiotic intervention; there may be a greater effect of the probiotic intervention in vaccinated than non vaccinated infants.

Before conducting subgroup analysis using the approach described above for pre-randomisation subgroups, we will first determine whether the intervention has an effect on the stratifying variable; this will be done by comparing the proportions within each subgroup by intervention arm using chi-squared tests. If there is evidence from this test that the intervention impacts on the distribution of participants across subgroup, then we will still conduct the formal test for effect modification as

described above but as sensitivity analysis we will investigate the use of propensity score methods to adjust for bias.

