2.2. Randomisation and blinding

Infants will be randomized in a 1:1 ratio to receive either intervention (*B. infantis* and *L. rhamnosus*) or control (placebo for *B. infantis* and *L. rhamnosus*) once daily for a period of 28 days. Randomisation will be stratified by site and by infant status (i.e. preterm, or term SGA), so that for each site there will be two randomisation lists, one for preterm infants and one for term SGA infants.

A statistician who is otherwise uninvolved with the study will generate the randomisation lists for each site using randomly permuted block sizes. This randomisation list will be embedded within the data

collection system. At the time of enrolment, a participant will be allocated to the next trial arm allocation on the randomisation list for their stratum.

Participants (i.e. infants and their care providers), hospital staff and all investigators (i.e. the site teams including the intervention, data collection, data management and data analysis teams, and the WHO team including the project managers and internal statistics team) will be blinded to the group allocation.

The intervention powder will be identical in appearance, consistency, taste and smell to the placebo powder. The intervention and placebo will be placed in foil sachets that are also identical in appearance and packaging. The sachets will be labelled, assembled into boxes and packs by an experienced packing team. The packing team will ensure that all labelling does not distinguish between placebo and intervention groups.

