For statistical analyses of continuous outcomes that require data to be normally distributed, the normality assumption of the data will be checked using graphical assessment of normality (Q-Q plot) and a Kolmogorov-Smirnov test for normality. If the data are found to be non-normal, medians (IQR) or geometric means (GMs) will be presented instead of means (SD). A log transformation will be applied to achieve normality and if not achieved, alternative tests such as the Wilcoxon rank sum test will be used to compare outcomes between trial arms. If normality is achieved through log transformation, then the parametric tests described above will be applied to the log transformed data.

Covariate adjustment

Adjustment for baseline covariates that are prognostic for the outcome has been shown to increase power to detect an intervention effect. For the primary outcomes, we therefore plan to further adjust for birth weight, receiving human milk at the time of randomisation (yes/no), receipt of any antibiotics at the time of randomisation (yes/no) and maternal education (none vs any), factors which have all been shown to be prognostic for the primary outcomes in their respective populations. Adjustment will be done within the binomial regression framework described above (or in the case of convergence issues, Poisson regression with robust standard errors).

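### The early-enteral-feeding subgroup has no category for infants first fed from 1 to under 2 hours after birth

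*SAP*

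**What the plan says.** SAP section 5.6 names the subgroup variable as "early initiation of enteral feeding (including mother's milk, donor milk, infant formula) (3 groups"), with the groups "within < 1hour, 2-< 24hour, 24+ hours after birth". The secondary objectives in section 1.2 use the same three groups.

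Section 5.6 presents its subgroups "listed according to whether the subgroups are defined pre-randomisation or post-randomisation", and this variable is in the pre-randomisation list. For that list the plan is to summarise results by subgroup and fit a model with an arm-by-subgroup interaction. For the post-randomisation list there is an earlier step: "we will first determine whether the intervention has an effect on the stratifying variable", by chi-squared test. If the arms differ, propensity-score methods follow as a sensitivity analysis.

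**The concern.** Subgroup categories should place every infant in exactly one group. Here an infant first fed at, say, 90 minutes has a known feeding time but no group.

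Two things are at stake. First, following the text drops these infants from an analysis of the primary outcomes that is itself a stated secondary objective. Second, someone will have to repair the definition at the analysis stage, and there are two natural repairs. Extending the first group to 2 hours counts these infants as early-fed. Starting the second group at 1 hour counts them with the later-fed. The same infants move from one side of the contrast to the other, so the choice should not be left until results by arm can be seen.

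**Working it through.** **Inputs.** The cut-points come from SAP sections 1.2 and 5.6. The expected enrolment of 9,500 preterm and 4,500 term SGA infants comes from section 2.3. The SAP has no figure of its own to reproduce on this point.

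**Step 1: coverage of the time axis.** Let *t* be hours from birth to first enteral feed. The stated groups are *t* < 1, 2 <= *t* < 24, and *t* >= 24. Assigning test times gives:

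| *t* (hours) | Group |
|---|---|
| 0, 0.5, 0.99 | <1 h |
| 1, 1.5, 1.99 | none |
| 2, 10, 23.99 | 2 to <24 h |
| 24, 48, 100 | 24+ h |

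The uncovered interval is 1 <= *t* < 2. Recording in whole hours would not close it, because a value of 1 is neither below 1 nor at least 2.

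**Step 2: is the gap intended?** The neighbouring groupings in section 5.6 are contiguous: <32 and 32 to <37 weeks for prematurity; <1.5, 1.5 to <2.5 and 2.5+ kg for birth weight. Nothing says that the 1-to-2-hour band is to be left out. The identical wording in two sections makes a text-extraction fault unlikely.

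**Step 3: does another rule catch these infants?** Section 5.5 uses complete cases, and adds multiple imputation where more than 10% of outcome data are missing. That concerns outcomes. It does not assign a group to an infant whose feeding time is known.

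**Step 4: how many?** The SAP gives no distribution of time to first feed. With an assumed share *s*, the number without a group is *s* × *N*:

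| Assumed *s* | Preterm (*N* = 9,500) | Term SGA (*N* = 4,500) |
|---|---|---|
| 2% | 190 | 90 |
| 5% | 475 | 225 |
| 10% | 950 | 450 |
| 20% | 1,900 | 900 |

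These are illustrations of scale, not estimates.

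**Step 5: timing relative to randomisation.** Section 2.2 says "At the time of enrolment, a participant will be allocated to the next trial arm allocation on the randomisation list for their stratum", and the SAP gives no age at enrolment in hours. Take an infant randomised at age *a* hours and not yet fed.

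- If *a* >= 24, the infant is already in the 24+ group at randomisation, whenever feeding then starts.
- If *a* < 24, the group is settled only after allocation.

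The pre-randomisation label is therefore in doubt only for infants of the second kind. The SAP does not show whether there are any.

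**The case against.** The strongest reply is that this is a boundary slip in one of 14 listed subgroup analyses (4 pre-randomisation, 10 post-randomisation). It touches no primary outcome, primary model or sample-size figure, and it can be put right before analysis if the time of first feed is recorded. All of that stands. It limits the weight of the point but does not remove the gap.

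A reader might go further and infer that the variable is misfiled as pre-randomisation, because section 5.3 adjusts for "receiving human milk at the time of randomisation (yes/no"), which suggests that some infants are unfed at that time. The SAP does not support that inference. The covariate concerns human milk, whereas the subgroup counts any enteral feed, formula included. A formula-fed infant is a no on the covariate and has still been fed. The enrolment window and any feeding rule for eligibility may be in the protocol, which was not available. The SAP also makes no claim that the pre-randomisation list is free of bias; it acknowledges bias for the other list and is silent on this one.

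A reader might also infer that other groupings leave infants out: that "feeding type at 1 month of age (3 groups): exclusive, predominant, partial" has no place for infants given no breast milk, or that the preterm SGA and AGA split has none for large-for-gestational-age infants. The SAP defines neither the feeding terms nor AGA, so exclusion is not shown in either case.

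**Conclusion.** The category gap is certain: as defined in sections 1.2 and 5.6, infants first fed from 1 to under 2 hours have no group and would drop out of this prespecified analysis. This rests on the text alone. Its size in infants is unknown, and the counts in the working depend wholly on the assumed share. The consequence is confined to this one subgroup analysis in each population.

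The timing question is conditional. It becomes a defect only if an infant can be randomised both before 24 hours of age and before a first feed, which the SAP neither states nor excludes.

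**What to change.** 1. Make the groups contiguous in both section 1.2 and section 5.6 before unblinding. One form is <1 h, 1 to <24 h and >=24 h, which keeps the stated 1-hour boundary. If a 2-hour cut was intended, write <2 h, 2 to <24 h and >=24 h. The sponsor should say which was meant.
2. Check how the data form captures first feeding. If it records a time, no new data are needed. If it uses the same three categories, the form needs the same correction, and infants already entered need their feeding time checked.
3. Confirm whether any infant can be randomised before 24 hours of age and before a first feed. If so, apply to this variable the comparison of subgroup proportions by arm, and the sensitivity analysis that follows from it, which section 5.6 already sets for post-randomisation subgroups. If not, one sentence saying so is enough.

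The cost is a few lines of SAP wording and, at most, a form correction. The primary analysis and sample size do not change.

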5.1. Primary outcome definitions

- Mortality from enrolment to 6 months of age among preterm infants: the proportion of infants who die from any cause from enrolment to 6 months of age.
- Underweight-free survival from enrolment to 6 months of age among term SGA infants: the proportion of infants with WAZ ≥ -2 at 6 months of age and who have not died.

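### Post-randomisation subgroups are measured within the outcome window: 6-month feeding type cannot be analysed for preterm mortality, and survival time shapes membership of the other nine

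*SAP*

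**What the plan says.** Section 5.6 opens with "We will assess whether the effect of probiotic supplementation on the primary outcomes differs in the following subgroups". The outcomes are those of section 5.1. For preterm infants it is "the proportion of infants who die from any cause from enrolment to 6 months of age". For term SGA infants it is a weight-for-age criterion met "at 6 months of age and who have not died", so a death is a failure.

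Of the 14 subgroup variables, four are listed as pre-randomisation and ten as post-randomisation:

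- three are feeding type at a fixed age: 1 month, "feeding type at 3 months of age (3 groups): exclusive, predominant, partial", and "feeding type at 6 months of age (3 groups): exclusive, predominant, partial";
- seven accumulate over the outcome window: "vaccination according to vaccine schedule from enrolment to 6 months (3 groups): fully vaccinated, partially vaccinated, not vaccinated", "receipt of antibiotics from enrolment to 6 months of age (2 groups): yes, no", and five any/none supplement variables (any micronutrient, iron, vitamin A, vitamin D, zinc).

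The section acknowledges that the post-randomisation analyses risk bias. As a safeguard, "we will first determine whether the intervention has an effect on the stratifying variable", by chi-squared test. If that test is positive, the interaction test is still run and propensity scores are to be explored as a sensitivity analysis.

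Nothing in the SAP says how an infant who dies before the variable is measured or completed is classified. The imputation rule in section 5.5 is triggered by missing outcomes, not by an undefined subgroup variable.

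**The concern.** A subgroup variable must be definable without knowing the outcome. Here death removes the infant from the feeding subgroups, and in the accumulating subgroups it cuts short the time in which exposure could occur. The outcome therefore helps to determine the subgroup.

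One planned analysis has no events at all. In others, mortality will differ sharply between the any and none groups even if the exposure does nothing. If probiotics act mainly early, for instance during the 28-day course, the risk ratio can also appear to differ between these groups when true modification is absent. Section 5.6 justifies the vaccination subgroup by a possibly greater effect in vaccinated infants. Under early benefit the artefact tends to run the other way, so the analysis could hide or reverse the pattern it was meant to find. The subgroup questions are stated secondary objectives (section 1.2).

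**Working it through.** **Inputs from the SAP.** Section 2.3: preterm control risk 10%, intervention 8%, two-sided 5% level, 90% power, 8,602 infants with outcome data. Section 2.2: 1:1 allocation. The SAP gives no timing of deaths, no supplement uptake and no start dates, so those below are assumptions.

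**The plan's own figure.** The two-proportion formula with pooled variance and no continuity correction gives 4,301 per arm, or 8,602. Dividing by 1 − 0.09 gives 9,453. Both match the SAP.

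**1. Feeding at 6 months, preterm mortality.** Expected deaths: 0.10 × 4,301 ≈ 430 and 0.08 × 4,301 ≈ 344, about 774 in all. None has a 6-month feeding type, so every cell is 0/N. The modified Poisson fallback in section 5.3 cannot help with zero events. This result needs no timing assumption.

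**2. Feeding at 1 month.** Let a share f of deaths precede 1 month. The remaining risk among infants alive then is p(1 − f)/(1 − pf). With f = 0.70, control is 0.030/0.930 = 3.2% and intervention 0.024/0.944 = 2.5%.

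| f (assumed) | Deaths left of 774 | Power for the overall arm contrast |
|---|---|---|
| 0.50 | about 387 | 65% |
| 0.70 | about 232 | 45% |
| 0.85 | about 116 | 26% |

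This is before any split into three groups. The 3-month version loses at least as many deaths.

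**3. Accumulating any/none variables.** Let u be uptake among survivors and a uptake among infants who die. Then

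- risk in *any* = pa / [pa + (1 − p)u]
- risk in *none* = p(1 − a) / [p(1 − a) + (1 − p)(1 − u)]

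Take u = 0.80 and a = 0.10, with no effect of the supplement:

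- control: 0.010/0.730 = 1.4% in *any*, 0.090/0.270 = 33.3% in *none*;
- intervention: 0.008/0.744 = 1.1% and 0.072/0.256 = 28.1%;
- risk ratios: 0.785 in *any*, 0.844 in *none*, against a true constant 0.80.

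Over u = 0.50 to 0.95 and a = 0.10 to 0.30, control mortality is about 1 to 6% in *any* and 13 to 67% in *none*. The risk ratio is about 0.79 in *any* and 0.81 to 0.92 in *none*.

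**4. The interaction test, by simulation.** Assumptions: 4,301 per arm, 70% ever exposed, start uniform on days 14 to 120, exposure independent of arm and prognosis, deaths uniform within the early (days 0 to 28) and late periods.

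- Scenario 1: early and late control risks 0.07 and 0.032, so 0.07 + 0.93 × 0.032 = 10.0%. Early risk ratio 0.708 and late 1.0, so 0.0496 + 0.9504 × 0.032 = 8.0%.
- Scenario 2: 0.05 and 0.053 (10.0%), early risk ratio 0.60 and late 1.0, giving 0.030 + 0.970 × 0.053 = 8.1%.

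| Setting | RR *any* | RR *none* | Interaction p < 0.05 |
|---|---|---|---|
| Scenario 1, all benefit early | 0.97 | 0.79 | about 20% |
| Scenario 2, all benefit early | 0.98–0.99 | 0.77 | about 37–38% |
| Constant RR 0.80, either scenario | 0.80–0.81 | 0.82–0.83 | about 5–6% |
| No effect | 1.0 | 1.0 | about 5% |

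The answer moves with the assumptions. With scenario 1 effects but exposure starting on days 0 to 7, rejection is about 5%; on days 0 to 28, about 8 to 10%. In a separate set-up (70% of deaths in month 1, start at 0.5 to 2.5 months), early benefit gives about 16% at 50% or 90% uptake. A constant 0.80 there gives 4% at 50% uptake but 12% at 90%.

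**5. The screen.** In step 3 the *any* share is 73.0% in control and 74.4% in intervention, although no infant's supplement use was changed; the gap comes only from fewer deaths. Over the ranges in step 3 the chi-squared test detects such a gap with about 6 to 66% power. A negative screen does not clear the analysis, and a positive one may simply reflect the mortality benefit.

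**The case against.** The plan is not naive. It separates pre- from post-randomisation subgroups, admits bias, gives a rationale and names a sensitivity method. These are secondary questions. That stands and limits the severity, but the safeguards ask whether treatment changes the subgroup variable, not whether death does. A propensity score cannot give a dead infant a 6-month feeding type.

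A reader might infer that all these interaction tests are invalid, or that a false finding of benefit only in unsupplemented infants is likely. The documents do not support that. Section 2.3 plans a single 20% relative reduction and says nothing about its timing. Under no effect the test keeps its nominal error, and under a constant effect it stays near 5% at moderate uptake. The larger figures need early benefit with late exposure.

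A reader might also infer that infants who die always fall into the none or unvaccinated group. That is a tendency only. Fatal illness may bring antibiotics first, moving deaths towards yes. Vaccination has a partial level, and its reference to the schedule could mean age-appropriate status.

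For term SGA infants, 6-month feeding can be analysed, because the outcome includes weight for age among survivors. Deaths, which count as failures, still have no subgroup.

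**Conclusion.** The point holds in two parts.

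- **Must fix:** 6-month feeding type against preterm mortality. It has no events among the classifiable infants and cannot be estimated. This follows from the definitions alone.
- **Should fix:** the other nine variables. Feeding at 1 and 3 months excludes earlier deaths, and for the seven accumulating variables survival time partly sets membership, so subgroup-specific risks are not interpretable. How far the interaction is distorted depends on the unknown timing of benefit, deaths and exposure: from about 5% rejection to about 38% in the settings examined.

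Confidence is high in the logic and moderate at best in the simulated sizes. The primary intention-to-treat estimates are not affected.

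**What to change.** - Delete the 6-month feeding subgroup for preterm mortality.
- For feeding at 1 and 3 months and for antibiotics, use the baseline variables already named in section 5.3 (human milk and antibiotics at randomisation). Alternatively use a landmark: classify infants alive at the landmark on data up to then, and count only later outcomes.
- For vaccination and the five supplement variables the SAP has no baseline version. Use a landmark, or report descriptively without an interaction p-value.
- State how deaths are classified in every remaining post-randomisation subgroup, including for term SGA underweight-free survival.
- Do not treat a negative chi-squared screen as clearance.

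The cost is SAP wording and modest programming. Some tables disappear. A landmark analysis answers a narrower question, later outcomes among those who survived to the landmark, with fewer events, and its arm comparison is no longer fully protected by randomisation if treatment alters early deaths. A baseline substitute asks about feeding or antibiotics at entry, not later.

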2.3. Sample size

The primary outcome for preterm infants is mortality at 6 months, which is assumed to be 10% in the control arm. A total of 8,602 preterm infants with data on this outcome would be needed for 90% power to detect a 20% relative reduction in mortality risk at 6 months in the intervention arm (i.e. 8% versus 10%), with 5% significance level. The 9,500 preterm infants expected to be enrolled across the 5 sites will allow 9% loss to follow up in determining the primary endpoint among preterm infants for a total of 9,453 preterm infants enrolled.

The primary outcome for term SGA infants is underweight free survival at 6 months, which is assumed to be 23% in the control arm. A total of 3,750 term SGA infants with data on this outcome would be needed for 90% power to detect a 20% relative improvement in underweight free survival in the intervention arm (i.e. 27.6% versus 23%), at 5% significance level. The 4,500 term SGA infants expected to be enrolled across the 5 sites will allow 16% loss to follow up in determining the primary endpoint among term SGA infants for a total of 4,465 term SGA infants enrolled.

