5.3. Analysis methods

Binary outcomes

The numerator, denominator and proportion with the outcome will be presented overall and by trial arm. A risk ratio comparing the proportion with the outcome in the intervention arm to the proportion

with the outcome in the control arm, along with a 95% confidence interval, will be calculated. As the randomisation is stratified by setting, the analysis will adjust for setting. This will be done using a binomial regression model with a log link function, and including both trial arm and setting as covariates. Binomial regression models can experience model convergence issues under certain circumstances; in this event we will instead use a modified Poisson regression approach with robust standard errors to estimate risk ratios and 95% confidence intervals.

Continuous outcomes

The number of participants, and the mean and standard deviation of the outcome will be presented overall and by trial arm. A difference in means comparing the intervention arm with the control arm, along with a 95% confidence interval will be calculated. As the randomisation is stratified by setting, the analysis will adjust for setting. This will be done using a multiple linear regression model, including trial arm and setting as covariates.

Rate outcomes

The number of episodes and the total person-time of follow-up will be presented overall and by trial arm. An incidence rate ratio comparing the intervention arm with the control arm, along with a 95% confidence interval, will be calculated. This will be done using Poisson regression with a random effects model to allow for multiple episodes occurring in some children, and including trial arm and setting as covariates. If the rate of the outcome varies over the follow-up time, then a Lexis expansion approach will be used to stratify the analysis, and allow the rate to vary by follow-up time period.

Checking assumptions

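### If the log-binomial model fails to converge and modified Poisson regression replaces it, the likelihood ratio tests for subgroup interactions become conservative; the SAP should name a robust Wald test for that case (minor)

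*SAP*

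**What the plan says.** Section 5.6 opens with "We will assess whether the effect of probiotic supplementation on the primary outcomes differs in the following subgroups" and lists four subgroup factors defined before randomisation and ten defined after it. Section 5.1 defines both primary outcomes as proportions. The method is "fitting a regression model including an interaction term between trial arm and subgroup indicator", with the instruction on testing: "Interaction terms will be assessed for strength of evidence against the null hypothesis of no effect modification, using likelihood ratio tests". The same approach is carried over to the post-randomisation factors.

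Section 5.6 does not name the regression model, so the framework for binary outcomes in section 5.3 applies. Its first choice is clear: "This will be done using a binomial regression model with a log link function". It then foresees failure, "Binomial regression models can experience model convergence issues under certain circumstances", and says "in this event we will instead use a modified Poisson regression approach with robust standard errors to estimate risk ratios". The paragraph on covariate adjustment repeats the same fallback: "or in the case of convergence issues, Poisson regression with robust standard errors". Nothing in the SAP changes the interaction test when the fallback is used.

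**The concern.** Modified Poisson regression fits a Poisson likelihood to 0/1 data, knowing the variance to be wrong, and repairs the standard errors afterwards with the sandwich estimator. A likelihood ratio test never sees that repair. It compares two Poisson likelihoods whose implied variance is p, whereas a binary outcome has variance p(1 - p). The statistic is therefore too small by a factor that depends on the outcome risk, and the p-value is too large.

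The text thus prescribes a test that does not suit one of its two prescribed models. What is at stake is the sensitivity of the interaction tests, which serve a listed secondary objective (section 1.2). The p-value from a subgroup factor whose model fell back would be conservative, while that from a factor whose model converged would be calibrated.

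**Working it through.** **Inputs from the SAP.** Section 2.3: preterm mortality 10% control and 8% intervention, 8,602 evaluable; term SGA underweight-free survival 23% control and 27.6% intervention, 3,750 evaluable; 90% power at the 5% level. Section 3.1: two-sided tests. Section 2.2: 1:1 allocation.

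**Planning figures reproduced.** Two proportions, pooled variance, no continuity correction:

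n per arm = [1.960 √(2p̄(1 - p̄)) + 1.282 √(p₁(1 - p₁) + p₂(1 - p₂))]² / (p₁ - p₂)²

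- Preterm: 4,301 per arm, 8,602 in total; 8,602 / 0.91 = 9,453 enrolled.
- Term SGA: 1,875 per arm, 3,750 in total; 3,750 / 0.84 = 4,465 enrolled.

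All four agree with section 2.3, so the rates are read correctly. The SAP gives no error rate for the interaction test itself.

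**Scale factor of the Poisson likelihood ratio.** With two subgroups and two arms, the interaction is a contrast of four log risks. Its true variance is the sum of (1 - p)/(np) over the four cells. The Poisson likelihood takes it to be the sum of 1/(np). The statistic therefore behaves as λ times chi-squared on 1 df, where

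λ = Σ[(1 - p)/(np)] / Σ[1/(np)], and true size = P(χ²₁ > 3.841/λ).

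**Equal subgroups with equal risks, no true interaction.**

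- Preterm: λ = (9 + 11.5)/(10 + 12.5) = 0.911; cut-off 3.841/0.911 = 4.216; size 0.040 (simulated 0.041).
- Term SGA: λ = (3.348 + 2.623)/(4.348 + 3.623) = 0.749; cut-off 5.128; size 0.024 (simulated 0.023).

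The simulations used 100,000 replicates per scenario. Read as a p-value, a result that deserves 0.05 would be reported as P(χ²₁ > 3.841λ), which is 0.061 for preterm and 0.090 for term SGA.

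**Unequal subgroup risks.** The SAP gives no risks by subgroup. These are assumptions, with risk ratio 0.8 (preterm) or 1.2 (term SGA) in both subgroups:

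| Population | Smaller subgroup: share, control risk | Control risk in the rest | λ | Size |
|---|---|---|---|---|
| Preterm | 20%, 25% | 6.25% | 0.861 | 0.035 |
| Preterm | 10%, 40% | 6.67% | 0.763 | 0.025 |
| Term SGA | 20%, 35% | 20% | 0.668 | 0.016 |
| Term SGA | 20%, 10% | 26.25% | 0.875 | 0.036 |

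**Power.** An interaction with 80% power by a valid 1-df test has non-centrality (1.960 + 0.842)² = 7.849. The probability that a non-central chi-squared with that parameter exceeds 3.841/λ is 0.77 (preterm) and 0.70 (term SGA) in the equal-risk case.

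**Valid comparators.** The robust Wald test in the modified Poisson model had simulated size 0.047 to 0.051 across the scenarios. The log-binomial likelihood ratio test had 0.048 (preterm) and 0.050 (term SGA) in 4,000 replicates. The SAP's first-choice combination is therefore calibrated, and so is the proposed replacement.

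**Three-category factors (2 df).** With one common risk in every cell, size = P(χ²₂ > 5.991/(1 - p)): 3.7% at p = 0.09, 3.6% at p = 0.10 and 1.8% at p = 0.25. A single scale factor holds only under equal risks, so these are indicative.

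**The case against.** The strongest reply is that the defect may never arise. It needs the log-binomial model to fail, and section 5.6 describes an interaction with a categorical indicator, to which section 5.3 adds setting. In simulations of that model (arm, five sites, subgroup and their interaction) at the SAP's sample sizes, under six assumed risk patterns that included a 50%-risk subgroup and a 1% sparse cell, all 1,200 log-binomial fits converged. Interaction terms and sparse cells alone did not trigger the fallback. Adding birth weight in continuous form and the other section 5.3 covariates gave failure rates from 2% to 100%, depending on the assumed slope. The SAP says neither that birth weight is continuous nor that those covariates enter the subgroup models. This part stands: the likelihood of the fallback cannot be judged from the document.

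It is also fair that section 5.6 speaks of strength of evidence and sets no 5% decision rule, and that the error cannot create false positives. Both limit the harm, but the reported p-value would still be too large.

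A reader might infer three further harms that the text does not support:

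- **Multiple imputation.** An ordinary likelihood ratio test needs a pooling rule on imputed data. However, section 5.5 makes complete cases the primary approach and does not say that imputation extends to the interaction tests.
- **Comparability.** Factors analysed by different models still estimate the same risk ratio. Only the interaction p-value is affected.
- **Conflict with confidence intervals.** The within-subgroup effects are not interaction tests, so their intervals need not agree with the interaction p-value even when that test is valid.

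**Conclusion.** The point holds as a conditional, minor one. Section 5.6 prescribes a likelihood ratio test in all cases, and section 5.3 prescribes a fallback model for which that test is miscalibrated. Given non-convergence, the true size of a nominal 5% 1-df test is about 4% for preterm mortality and 2.4% for term SGA underweight-free survival; unequal subgroup risks move both. The power loss is about 3 and 10 percentage points from 80%.

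The equal-risk figures rest on the section 2.3 rates, two subgroups of equal size and no allowance for setting in the variance formula. The unequal-risk range rests on assumed subgroup shares and risks. The 5% level is a benchmark borrowed from section 2.3.

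A reader might infer that the planned interaction tests are invalid as they stand, or that the fallback is bound to be used. Neither follows: the test is valid for every log-binomial model that converges, and the SAP leaves open the details that would make failure likely. The primary effect estimates and their confidence intervals are not affected.

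**What to change.** Add a sentence to section 5.6: when modified Poisson regression is used, interaction terms are tested by a joint Wald test with the robust variance; the likelihood ratio test is kept for log-binomial models that converge. Using the robust Wald test throughout is simpler still, since every subgroup factor then has the same test whichever model was fitted.

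It would help to state in the same place whether the section 5.3 covariates enter the subgroup models and in what form birth weight is used, because these settle how often the fallback is likely to be needed.

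The cost is a sentence or two in the SAP and one post-estimation command in the analysis code. No data collection or sample size changes.
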